5.3.3 Contrast Sensitivity

Contrast sensitivity testing is conducted at [Redacted]

[Redacted] 12.0 CPD for mesopic testing. [Redacted]

[Redacted text block]

The following table presents the manufacturer’s recommended log contrast sensitivity norms corresponding to the recorded scores of -1, 0, or 1-8.

[Redacted text block]

[Redacted text block]

[Redacted text block]

[Redacted text block]

[Redacted text block]

[Redacted text block]

[Redacted text block]

[Redacted text block]

[Redacted text block]

[Redacted text block]

[REDACTED]

[REDACTED]

[REDACTED]

[REDACTED]

[REDACTED]

[REDACTED]

[REDACTED]

[REDACTED]

[REDACTED]

5.4 Interim Analysis for Safety

Not Applicable.

[REDACTED]

[REDACTED]

7 Sample Size and Power Calculations

Effectiveness

The proposed sample size (N = 234; 130 Bilateral EDF IOL and 104 Bilateral Monofocal IOL) provides >99% power for the superiority hypothesis test on mean monocular DCIVA (66 cm) when tested at the 0.025 level of significance (one-sided). This assessment assumes:

- Difference in DCIVA (66 cm) [logMAR]: Mean (SD) = -0.12 (0.18)

The proposed sample size provides 74% power for the non-inferiority hypothesis test with respect to mean monocular BCDVA (4 m) when tested at the 0.025 level of significance (one-sided) with a non-inferiority margin of 0.10 logMAR assuming:

- Difference in BCDVA (4 m) [logMAR]: Mean (SD) = 0.04 (0.16)

The proposed sample size provides >99% power for the superiority hypothesis test on mean monocular DCNVA (40 cm) when tested at the 0.025 level of significance (one-sided). This assessment assumes:

- Difference in DCNVA (40 cm) [logMAR]: Mean (SD) = -0.12 (0.18)

The proposed sample size provides 74% power for the non-inferiority hypothesis test with respect to mean monocular mesopic contrast sensitivity value when tested at the 0.025 level of significance (one-sided) with a non-inferiority margin of -0.15 log unit assuming:

- Difference in contrast sensitivity [log unit]: Mean (SD) = -0.02 (0.38)

The expected sample size (N = 131) will provide 84% power, with $\alpha=0.025$, 1-sided, to detect a difference of 25% in proportion of subjects who respond “Never” to Q1 and Q3 of the spectacles use questionnaire, respectively, assuming

- Proportion of subjects who respond “Never” is 50% in the ACRYSOF IQ EDF IOL group.

Approximately 260 subjects will be randomized to achieve 234 subjects who complete the study, assuming a 10% drop-out rate. It is expected that approximately 131 subjects will respond to spectacle use questionnaire in this study.

Adverse Events

For any event where zero incidence is observed in 130 operative eyes with ACRYSOF IQ EDF IOL, the one-sided exact 95% upper confidence limit is less than 2.3%. Thus, with 95% confidence the true adverse event rate is less than 2.3%.

8 References

5. Miettinen OS and Nurminen M. Comparative analysis of two rates. *Statistics in Medicine*, 4:213-226 (1985).

[Redacted]

[Redacted]

[Redacted]

[Redacted]

[Redacted]

[Redacted]

[Redacted]

[Redacted]

[Redacted]

[Redacted]

[Redacted]

[Redacted]

[Redacted]

[Redacted]

[Redacted]

[Redacted]

[Redacted]

[Redacted]

[Redacted]

[Redacted]

[Redacted]

[Redacted]

[Redacted]

[Redacted]

[Redacted]

[Redacted]

[Redacted]

[Redacted]

- [Redacted]
- [Redacted]

[Redacted]

[Redacted]

[Redacted]

[Redacted]

[Redacted]

[Redacted]

[Redacted]

- [Redacted]

- [Redacted]

[Redacted]

Visit	Visit 0 Pre-Op	Visit 00: OP ¹	Visit 1	Visit 2	Visit 00A: OP ²	Visit 1A	Visit 2A	Visit 3A	Visit 4A ³	Visit 5A ³	Early Exit
Eye	Both Eyes	1 st Eye	1 st Eye	1 st Eye	2 nd Eye	2 nd Eye	2 nd Eye	Both Eyes	Both Eyes	Both Eyes	
Day Number	Day -28-0	Surgery	Day 1-2	Day 7-14	Surgery	Day 1-2	Day 7-14	Day 30-60	Day 70-100	Day 120-180	N/A
[REDACTED]											
Incision Location ⁷		X			X						
Final Incision Size ⁷		X			X						
[REDACTED]											
[REDACTED]											
[REDACTED]											
[REDACTED]											
[REDACTED]											
[REDACTED]											
Adverse Events	X	X	X	X	X	X	X	X	X	X	X
Secondary Surgical Interventions		X	X	X	X	X	X	X	X	X	X
Device Deficiencies		X	X	X	X	X	X	X	X	X	X

¹ Visit 00 (1st eye surgery) must occur within 28 calendar days from Pre-Operative Visit (Visit 0).

² Visit 00A (2nd eye surgery) must occur after a minimum of 7 calendar days and a maximum of 28 calendar days after Visit 00 (1st eye surgery).

³ If necessary Visits 4A and 5A may be completed over 2 days within a two week period. All visits must be completed within the specified visit window.

⁴ In women of child bearing potential only.

⁵ Monocular (bilaterally) and binocular testing.

⁶ Data is reported in EDC at the surgical visit, but may be collected at a previous visit.

⁷ Captured in source. Not collected in EDC.

Date/Time (mm/dd/yyyy GMT):	Signed by:	Justification:
[REDACTED]	[REDACTED]	[REDACTED]
[REDACTED]	[REDACTED]	[REDACTED]
[REDACTED]	[REDACTED]	[REDACTED]
[REDACTED]	[REDACTED]	[REDACTED]

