Descriptive summaries (counts and percentages) for specific AEs will be presented by IOL group. The one-sided exact 95% lower confidence limit of incidence rates (proportion of eyes with events) observed for each IOL group will be compared to the cumulative and persistent adverse event SPE rates. In addition to SPE rates predefined in IS EN ISO 11979 7, the rate of adverse events that may be specifically related to ACRYSOF IQ EDF IOL design features; and any other significant events will be provided. These rates will be accompanied by two-sided exact 95% confidence intervals.

Sample Size Justification:

Effectiveness

The proposed sample size (N = 234; 130 Bilateral EDF IOL and 104 Bilateral Monofocal IOL) provides >99% power for the superiority hypothesis test on mean monocular DCIVA (66 cm) when tested at the 0.025 level of significance (one-sided). This assessment assumes:

- Difference in DCIVA (66 cm) [logMAR]: Mean (SD) = -0.12 (0.18)

The proposed sample size provides 81% power for the non-inferiority hypothesis with respect to mean monocular BCDVA (4 m) when tested at the 0.025 level of significance (one-sided) with a non-inferiority margin of 0.10 logMAR assuming:

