13.11 Sample Size Justification

Effectiveness

The proposed sample size (N = 234; 130 Bilateral ACRYSOF IQ EDF IOL and 104 Bilateral ACRYSOF IQ Monofocal IOL) provides >99% power for the superiority hypothesis test on mean monocular DCIVA (66 cm) when tested at the 0.025 level of significance (one-sided) assuming the difference in means is -0.12 logMAR (SD = 0.18).

The proposed sample size (N = 234; 130 Bilateral ACRYSOF IQ EDF IOL and 104 Bilateral ACRYSOF IQ Monofocal IOL) provides 81% power for the non-inferiority

hypothesis with respect to mean monocular BCDVA (4 m) when tested at the 0.025 level of significance (one-sided) with a non-inferiority margin of 0.10 logMAR assuming the difference in means is 0.04 logMAR (SD = 0.16).

The proposed sample size (N = 234; 130 Bilateral ACRYSOF IQ EDF IOL and 104 Bilateral ACRYSOF IQ Monofocal IOL) provides >99% power for the superiority hypothesis test on mean monocular DCNVA (40 cm) when tested at the 0.025 level of significance (one-sided) assuming the difference in means is -0.12 logMAR (SD = 0.18).

The proposed sample size (N = 234; 130 Bilateral ACRYSOF IQ EDF IOL and 104 Bilateral ACRYSOF IQ Monofocal IOL) provides 74% power for the non-inferiority hypothesis with respect to mean monocular mesopic contrast sensitivity value when tested at the 0.025 level of significance (one-sided) with a non-inferiority margin of -0.15 log unit assuming the difference in mean is -0.02 log unit (SD = 0.38).

The expected sample size (N = 131) will provide 84% power, with $\alpha=0.025$, 1-sided, to detect a difference of 25% in proportion of subjects who respond “Never” to Q1 and Q3 of the spectacles use questionnaire respectively, assuming a 50% rate in the ACRYSOF IQ EDF IOL group.

Approximately 260 subjects will be randomized to achieve 234 subjects who complete the study. It is expected that approximately 131 subjects will respond to spectacle use questionnaire in this study.

Adverse Events

For any event where zero incidences is observed in 130 operative eyes with ACRYSOF IQ EDF IOL, the upper limit of the 95% 1-sided exact binomial confidence interval is less than 2.3%. Thus, with 95% confidence the true adverse event rate is less than 2.3%.

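### SAP Section 7 states 74% power for the BCDVA non-inferiority test; its own inputs give 81%, the figure the protocol states

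*SAP*

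**What the plan says.** SAP Section 7 sets the sample size in its first sentence on effectiveness, which concerns DCIVA: "The proposed sample size (N = 234; 130 Bilateral EDF IOL and 104 Bilateral Monofocal IOL) provides >99% power". On BCDVA it then states: "The proposed sample size provides 74% power for the non-inferiority hypothesis test with respect to mean monocular BCDVA (4 m"). That statement carries a one-sided level of 0.025 and a margin of 0.10 logMAR. The assumed effect follows as a bullet: "Difference in BCDVA (4 m) [logMAR]: Mean (SD) = 0.04 (0.16").

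The protocol gives a different power for the same test. Its Section 3 summary reads: "The proposed sample size provides 81% power for the non-inferiority hypothesis with respect to mean monocular BCDVA (4 m"), with the same difference and SD. Section 13.11 repeats the figure ("provides 81% power for the non-inferiority") and pairs it with the same assumption, namely that the "difference in means is 0.04 logMAR (SD = 0.16"). The sample size, level and margin there are also the SAP's.

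Further down, SAP Section 7 uses 74% again for another endpoint: "The proposed sample size provides 74% power for the non-inferiority hypothesis test with respect to mean monocular mesopic contrast sensitivity value". The protocol gives 74% for that endpoint too.

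**The concern.** Two current documents give different powers for one test from one set of inputs, so at least one figure is wrong. A reader comparing them would ask whether an assumption changed between protocol and SAP. The visible text does not answer that.

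BCDVA is the first secondary hypothesis and one of the Month 3 tests that must succeed before Month 6 testing goes ahead (SAP Section 4.4). Its stated power therefore describes a gate in the testing sequence. At 74% the gate looks weaker than it was planned to be.

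**Working it through.** **Inputs for BCDVA (SAP Section 7; identical in Protocol Sections 3 and 13.11)**

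- Completers: 130 test, 104 control
- Level: one-sided 0.025
- Margin: 0.10 logMAR
- Assumed true difference: 0.04 logMAR
- SD: 0.16
- Test: one-sided 97.5% upper limit from a two-sample t-test, compared with 0.10 (SAP Section 4.3.2.1)

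**Power from these inputs**

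- Standard error = 0.16 × √(1/130 + 1/104) = 0.16 × 0.13156 = 0.02105
- Noncentrality = (0.10 − 0.04) / 0.02105 = 2.850, with 130 + 104 − 2 = 232 degrees of freedom
- Normal approximation: Φ(2.850 − 1.960) = Φ(0.890) = 81.3%
- Noncentral t: 81.0%
- Simulation of the confidence-limit rule (20,000 trials): 81.1%

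The protocol's 81% reproduces. The SAP's 74% does not: 81 − 74 = 7 points, more than rounding or choice of formula explains.

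**The same method on the neighbouring figures**

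- Contrast sensitivity (difference −0.02, SD 0.38, margin −0.15): noncentrality = (0.15 − 0.02) / (0.38 × 0.13156) = 2.600. Power is 73.6% by noncentral t and 73.9% by the normal approximation, so the stated 74% is right.
- DCIVA (difference −0.12, SD 0.18): noncentrality = 0.12 / (0.18 × 0.13156) = 5.07. Power is 99.9%, which agrees with the stated >99%. DCNVA has the same inputs and the same result.

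Of the four t-test powers in the section, only the BCDVA figure fails.

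**Could another reading give 74%?** (noncentral t)

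| Reading | BCDVA power |
|---|---|
| As stated: 130/104, one-sided 0.025 | 81.0% |
| Equal split, 117/117 | 81.5% |
| All 260 randomized, 144/116 | 85.0% |
| A further 10% off the 234, 117/94 | 76.9% |
| One-sided 0.05 | 88.4% |
| One-sided 0.0125 | 72.4% |

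Two readings lower the power. The 117/94 case removes dropout twice, because 234 is already the number of completers after a 10% loss from 260. The 0.0125 case contradicts the stated level and the 97.5% limit. Neither rounds to 74%.

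**What 74% would require, changing one input at a time**

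- SD about 0.174 instead of 0.16, or
- true difference about 0.045 instead of 0.04, or
- one-sided level about 0.0142 instead of 0.025, or
- about 198 completers (110/88, power 74.2%) instead of 234.

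None of these values appears in the documents.

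**The case against.** The strongest objection concerns weight. Power is a planning figure. The test, the margin, the confidence limit and the 234 completers are the same whichever number is printed. The error is on the cautious side, so nobody is led to rely too much on the design. The SAP's executive summary also ties study success to the primary objective alone. All of this stands, and it is why the point is minor.

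A second objection is that the correction assumes the stated power is wrong and the inputs are right. The SAP's revision history is redacted, so the SAP alone cannot rule out an outdated input; an SD of about 0.174, for example, would give 74%. This carries little weight, because two protocol sections state the same inputs and pair them with 81%. It is still reasonable for the sponsor to confirm the inputs when making the change.

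Third, the idea that 74% was copied from the contrast sensitivity line is an inference. The finding does not depend on it.

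**Conclusion.** The concern holds, as a minor error. On the SAP's own inputs, BCDVA power is 81%, not 74%; the SAP is 7 percentage points too low and disagrees with both protocol statements. This rests on the stated difference, SD, margin, level and completer numbers, and on an equal-variance two-sample t-test in the first implanted eye. The affected sentence and its inputs are complete, current text, so neither redaction nor superseded wording explains the mismatch. No conclusion about the adequacy of the design changes.

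**What to change.** In SAP Section 7, change the BCDVA (4 m) power from 74% to 81%, after the sponsor confirms that the stated difference (0.04) and SD (0.16) are the intended ones. Leave the 74% for mesopic contrast sensitivity unchanged. The protocol needs no edit. The cost is one number in the SAP text; enrolment, margin, significance level, testing order and decision rules all stay as they are.

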9 SUBJECT POPULATION

The study population consists of male and female subjects 22 years of age and older with a diagnosis of cataract in both eyes requiring surgery with implantation of a monofocal IOL in the capsular bag. It is aimed to randomize approximately 260 subjects in approximately 16 centers globally, with a target of approximately 16 subjects randomized per site. Site specific targets may be adjusted based on individual site capabilities. Enrollment projections are as follows:

- 260 subjects to be randomized (10% discontinuation rate is expected)
- 234 subjects to successfully complete the final study visit (Visit 5A)
 - 130 subjects in the Model DFT015 arm

- 104 subjects in the Model SN60WF arm

Check all entry criteria at Screening/Visit 0 and at both surgical visits (Visit 00, Visit 00A). If a subject is excluded post randomization and prior to 1st eye surgery (IOL does not come in contact with the eye), the subject should be discontinued from participation in the study. Refer to Section 11.11 Discontinued Subjects for further details.

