Below is a list of study procedures to be completed at Visit 4A. All assessments must be documented in source documentation and eCRF (if applicable). It is recommended that procedures are performed in the order described below unless otherwise stated. If a subject appears fatigued, or requests a break from testing, provide a rest. If the visit is conducted

over multiple sessions or days, seek advice from Alcon staff regarding best practices. For example:

- Conducting primary and secondary outcome assessments day 1; and
 - Conducting distance, intermediate and near VA testing in an early session and defocus testing in a later session on day 1.
1. Record changes in medical/ocular history and ocular and non-ocular concomitant medications.

2. Measure photopic pupil size. *[Both Eyes, Bilateral]*

3. [Redacted]

4. Measure and record monocular [Redacted] and BCDVA under photopic conditions at 4 m. *[Both Eyes, Bilateral]*

5. Perform monocular defocus curve testing. *[Both Eyes, Bilateral]*

[Redacted]

7. Measure and record monocular [Redacted] and DCIVA under photopic conditions at 66 cm. *[Both Eyes, Bilateral]*

8. Measure and record monocular [Redacted] and DCNVA under photopic conditions at 40 cm. *[Both Eyes, Bilateral]*

[Redacted]

[Redacted]

[Redacted]

[Redacted]

[REDACTED]

[REDACTED]

[REDACTED]

[REDACTED]

[REDACTED]

[REDACTED]

17. Record any adverse events including SSIs. Refer to Section 12 for further detail.

18. Record any device deficiencies. Refer to Section 12 for further detail.

11.7 6-Month Postoperative Visit (Visit 5A)

Visit 5A: 120-180 Days Post 2nd Eye Implantation, Bilateral with Binocular Testing

Below is a list of study procedures to be completed at Visit 5A. All assessments must be documented in source documentation and eCRF (if applicable). It is recommended that procedures are performed in the order described below unless otherwise stated. If a subject appears fatigued, or requests a break from testing, provide a rest. If the visit is conducted over multiple sessions or days, seek advice from Alcon staff regarding best practices. For example:

- Conducting primary and secondary outcome assessments day 1; and
 - Conducting distance, intermediate and near VA testing in an early session and defocus testing in a later session on day 1.
1. Provide questionnaires ([REDACTED] Spectacle Use) to the subject for completion. The questionnaires should be completed by the subject prior to administration of any other assessment.

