For the fifth secondary effectiveness endpoint, a two-sided 95% confidence interval for the difference in proportions (ACRYSOF IQ EDF IOL – ACRYSOF IQ Monofocal IOL) will be calculated using the Miettinen-Nurminen method [5], and ACRYSOF IQ EDF IOL will be determined to be superior to ACRYSOF IQ Monofocal IOL if the lower boundary of the confidence interval is greater than zero. This is equivalent to using a type I error rate of 2.5%, 1-sided. Response to Q3 of spectacle use questionnaire will be tested followed by response to Q1 of spectacle use questionnaire.

The following SAS pseudocode will be used to estimate the difference in proportions and the corresponding two-sided 95% confidence interval.

```

proc freq data=IOLSAT;
  tables IOL*IOLSATQ1 /riskdiff(CL= MN) alpha = 0.05;
  * MN = Miettinen and Nurminen inverted score test;
  ods output PdiffCLs=CI_by_MN;
run;

```

In addition, the frequencies of responses to each item in the spectacle use questionnaire will be summarized by IOL group and visit with counts and percentages.

[REDACTED]

[REDACTED]

[REDACTED]

[REDACTED]

[REDACTED]

[REDACTED]

[REDACTED]

[REDACTED]

[REDACTED]

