4.4 Multiplicity Strategy

Overall type I error will be maintained at 0.05 level for the Month 3/Visit 4A (70-100 day post 2nd eye implantation) analyses using the sequential testing approach summarized in the figure below.

The following primary and secondary effectiveness analyses will be performed on the Month 6/Visit 5A (120-180 day post 2nd eye implantation) data using the sequential testing approach summarized in the figure below if the primary and both secondary null hypotheses are rejected for the Month 3/Visit 4A (70-100 day post 2nd eye implantation) analysis. If any null hypothesis is not rejected, no further hypothesis testing will be performed.

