4.6 Handling of Missing Data

The AAS and BAS do not include any imputed values. Although the influence of missing data is expected to be minimal, the following sensitivity analyses will be conducted to assess the impact of missing data on the conclusions from the primary endpoint analysis.

1. Multiple imputation (with a fully conditional specification) method will be used to impute and estimate the treatment effect.
2. The sensitivity of inferences to departures from the MAR assumption will be examined using a pattern-mixture model approach (with a control-based pattern imputation^[4]).

Sensitivity Analysis 1:

A fully conditional specification (FCS) method will be used to impute missing DCIVA values at all visits in a data set with an arbitrary missing pattern. The FCS method uses a separate conditional distribution for each imputed variable.

The following SAS pseudo-code with the PROC MI procedure will be used to impute missing DCIVA values using FCS method:

```

/* multiple imputation w/ MAR assumption          */
/* DCIVA1-DCIVA4 should be in parallel structure */
proc mi data=mi_in seed=1001 nimpute=10 mu0=.3 .2 .1 .0 out=mi_out1;
  fcs nbiter=20 reg; *reg(/details);
  var DCIVA1 DCIVA2 DCIVA3 DCIVA4;
run;

/* run glm on each iteration of mi */
proc glm data=mi_out1;
  by _Imputation_;
  class LENS_MODEL;
  model DCIVA4 = LENS_MODEL;
  estimate 'Trt_Eff' LENS_MODEL 1 -1;
  ods output Estimates = glm_out1;
run;

/* no need to sort if there is only one parameter being estimated */

```

```

proc sort data=glm_out1;
  by parameter _imputation_;
run;

/* generate estimates and CIs from multiple imputation */
proc mianalyze data=glm_out1;
  by parameter;
  modeleffects estimate;
  stderr stderr;
  ods output ParameterEstimates = Param_out1;
run;

```

Sensitivity Analysis 2:

The sensitivity of inferences to departures from the MAR assumption will be examined using a pattern-mixture model approach with a control-based pattern imputation.

The following SAS pseudo-code with the PROC MI procedure will be used to implement the control-based pattern imputation:

```

/* multiple imputation w/ MNAR assumption */
/* DCIVA1-DCIVA4 should be in parallel structure */
proc mi data=mi_in seed=1001 nimpute=10 mu0=.3 .2 .1 .0 out=mi_out2;
  class LENS_MODEL;
  fcs nbiter=20 reg; *reg(/details);
  mnar model( DCIVA1 DCIVA2 DCIVA3 DCIVA4 /modelobs=(LENS_MODEL='SN60WF'));
  var DCIVA1 DCIVA2 DCIVA3 DCIVA4;
run;

/* run glm on each iteration of mi */

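### Does the spectacle-use superiority test need a planned non-response analysis because only about 131 answers are expected against 234 completers?

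*SAP*

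**What the plan says.** - **Attendance.** Protocol 9 plans for "234 subjects to successfully complete the final study visit (Visit 5A"), made up of 130 test-lens and 104 control-lens subjects.
- **Questionnaire.** Protocol 11.7 hands it out at Visit 5A and names no subset: "The questionnaires should be completed by the subject prior to administration of any other assessment". The schedule in Protocol 5 and the list in Protocol 11.8 also give it at Early Exit.
- **Expected answers.** SAP 7 and Protocol 13.11 agree: "It is expected that approximately 131 subjects will respond to spectacle use questionnaire in this study". Both state 84% power for 131 at one-sided 0.025, with 50% *Never* on the test lens and a difference of 25 points.
- **Formal test.** SAP 4.3.2.5 uses a two-sided 95% Miettinen-Nurminen interval. The order is fixed: "Response to Q3 of spectacle use questionnaire will be tested followed by response to Q1 of spectacle use questionnaire". The code line "tables IOL*IOLSATQ1 /riskdiff(CL= MN) alpha = 0.05" works on the answers available. The same section also plans counts and percentages of the answers to every item, by lens group and visit.
- **Missing data.** SAP 4.6 states: "The AAS and BAS do not include any imputed values". It then plans two analyses, multiple imputation and a control-based pattern-mixture model, with this scope: "sensitivity analyses will be conducted to assess the impact of missing data on the conclusions from the primary endpoint analysis".
- **Place in the testing.** SAP 4.4 allows Month 6 testing only after the Month 3 hypotheses are rejected, and adds: "If any null hypothesis is not rejected, no further hypothesis testing will be performed". The SAP Executive Summary rests study success on the primary objective.

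**The concern.** Set side by side, the figures look uneven. The primary endpoint has a planned drop-out of 10% and two missing-data checks. The questionnaire endpoint appears to have answers from little more than half of the completers, and the readable SAP gives it no check.

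The test can support a formal statement that more test-lens subjects never need spectacles. If many subjects were asked and did not answer, and those who answered differ from those who did not, the respondents-only difference could misstate the effect. A reader of the report could not tell how far the claim depends on who replied. What is at stake is a secondary claim. The primary endpoint and the success rule are not touched.

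**Working it through.** **Inputs.** 130 and 104 completers, 131 respondents, 5:4 allocation, 50% against 25%, and one-sided 0.025 (SAP 7, SAP 1.3, Protocol 9). Splitting 131 by 5:4 gives 73 and 58, which assumes equal response by arm. The rates among non-respondents are assumptions; no document gives one.

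**1. The plan's own figure.** Pooled rate = (73 × 0.50 + 58 × 0.25)/131 = 51/131 = 0.389.
- Null SE = √[0.389 × 0.611 × (1/73 + 1/58)] = 0.0858.
- Alternative SE = √(0.25/73 + 0.1875/58) = 0.0816.
- Power = Φ[(0.25 − 1.96 × 0.0858)/0.0816] = Φ(1.00) = 84.2%.

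Exact enumeration of the Miettinen-Nurminen score test also gives 84.2%. The stated 84% therefore already allows for 131 answers, and there is no power error.

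**2. The apparent gap.** 131/234 = 56.0%, and 234 − 131 = 103, or 44.0%. Split by arm this is 130 − 73 = 57 and 104 − 58 = 46.

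**3. If all 103 were due to answer.** Let a and b be the *Never* rates among test and control non-respondents. The completed counts are x₁ + 57a of 130 and x₂ + 46b of 104. These are expected counts, with no imputation variance. Two results that are significant among respondents serve as examples:

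| Assumption (a, b) | 37/73 vs 14/58 | 34/73 vs 15/58 |
|---|---|---|
| Respondents only | +26.5 (9.9 to 41.6) | +20.7 (4.0 to 36.0) |
| 0%, 0% | +15.0 (4.5 to 25.1) | +11.7 (1.3 to 21.8) |
| 25%, 25% | +14.9 (2.8 to 26.4) | +11.6 (−0.4 to 23.2) |
| 15%, 25% | +10.5 (−1.4 to 21.9) | +7.3 (−4.6 to 18.7) |
| 35%, 25% | +19.3 (7.1 to 30.8) | +16.0 (3.8 to 27.6) |
| Same as respondents | +26.5 (14.2 to 38.0) | +20.7 (8.3 to 32.3) |

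**4. Share of significant respondent results that would not hold.** This is enumerated over Binomial(73, 0.50) × Binomial(58, 0.25). The middle column takes about half of the 103 as due (28 test and 23 control, so 101 and 81 in all).

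| a, b | All 103 due (130/104) | About half due (101/81) | None due |
|---|---|---|---|
| 0%, 0% | 7% | 4% | 0% |
| 25%, 25% | 21% | 10% | 0% |
| 37.5%, 37.5% | 25% | 12% | 0% |
| 15%, 25% (reversed effect) | 63% | 29% | 0% |
| 30%, 25% | 3.7% | 2.2% | 0% |
| 35%, 25% | 0% | 0% | 0% |

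The large shares need non-respondents to get no benefit from the lens, or harm. With 10 of the planned 25 points of benefit (35% against 25%), no significant result is lost. The whole table falls to zero if the 103 were never due the questionnaire.

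**5. What the documents say about the 103.** They give a number of expected respondents and nothing more. They do not call it a fraction of completers, and some answers may come from Early Exit visits. Protocol 13.4 still counts three hypothesis tests, while the hypotheses and test orders set out beneath it come to seven: intermediate, distance and near acuity, contrast sensitivity without and with glare, Q3 and Q1. That fits a questionnaire test added after the study began, with an administrative reason for 131. It does not prove it.

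**The case for a change.** The best case for acting is that SAP 4.6 can be read in full, expects missing data to matter little, and covers the primary endpoint only. Nothing readable says what to do with an unanswered questionnaire. The example of 34/73 against 15/58 loses superiority when non-respondents merely show no difference between arms, so no reversal is needed. Selective response could also inflate the error rate. With a true 25% in both arms, and response that depends on the answer in the test arm only, the one-sided error rises from 2.3% to 4.5% (61% of *Never* subjects respond against 54% of others) or 13.6% (71% against 50%). The added tables cost little, and they carry more weight if fixed before unmasking.

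Some of this stands. The readable SAP has no check for this endpoint, and the reason for 131 is not given. Three points limit it.

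- Selection confined to one arm needs a mechanism. Subjects stay masked throughout (Protocol 10.4). If reply depends on the answer in the same way in both arms, respondents' rates stay equal when there is no lens effect.
- Respondent counts by arm are already planned in SAP 4.3.2.5. A response rate needs only the number who were due the questionnaire.
- Protocol 13.5 on missing data, the SAP revision history and parts of the SAP are blacked out. The absence of a check, or of a reason, can be asserted only for the text that can be read.

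**Conclusion.** No change to the plan follows. The 84% power is correct for 131 answers, and the Miettinen-Nurminen test of respondents is a clear and reproducible formal analysis. Non-response tables would be supportive only. They would not alter the test, the sample size, the error control or the success rule.

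Whether there is any non-response to examine depends on a fact that cannot be read. If the 103 were never due the questionnaire, the effect on the claim is nil. If all were due, the share of significant results that would not hold runs from 0% to 63% across the assumed rates, and 63% needs a reversed lens effect. These shares rest on a 73/58 split, the planning rates of 50% and 25%, and expected counts without imputation variance.

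A sentence saying why 131 are expected and who is due the questionnaire would help a reader. If some of those due fail to answer, analysts can report the denominators by arm and a simple sensitivity analysis from data already collected. That is optional reporting.
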